8.11 Anti-Therapeutic Antibodies (ATA) Analysis

Serum Collection for Anti-therapeutic Antibodies (ATA) Analysis

Blood samples at baseline, and at between 35 to 42 days after the first dose of rhNGF will taken from all subjects for the ATA determination.

The concentration of ATA will be assessed from individual serum samples of all subjects.

All blood samples will be taken by either direct stick or an indwelling cannula inserted in a forearm vein. On the days of ATA determination, a cannula will be inserted. Any missing blood draws must be reported on the respective eCRF comment sheet.

A validated ELISA assay performed by the provider will be used for anti-therapeutic antibodies (ATA) detection:

Swiss BioQuant AG
[name]
[name]

The processing, storage and shipment instructions for the immunocnicity samples obtained in this Study will be provided in the Research Specimen Manual.

Briefly: each blood (7.5 mL) sample will be transferred to a polypropylene test tube and kept undisturbed at room temperature (approximately 15-30 minutes) to allow coagulation. The samples will then be centrifuged at 1900 g for 15 minutes at $20 \pm 5^{\circ}\text{C}$ and the serum obtained from each sample (at least 3.5 mL) will be distributed to two fresh polypropylene test tubes. two aliquots of 1.7 mL each of serum will be immediately frozen in dry ice and then stored at $-70 \pm 10^{\circ}\text{C}$ until shipment to the Analytical LAB for the determination by ELISA validated method.

The aliquots will be sent to the bioanalytical laboratory using a specialized provider (e.g. Wourld Courier) in frozen condition . The temperature will be monitored by temperature log during the shipment period.

The serum concentrations of ATA will be provided by the bioanalytical laboratory in a separate report and incorporated into the final CSR as an appendix.

The remaining aliquots of serum samples will be stored up to one year after CSR finalization.

8.11.1 Total volume of blood to be taken from each subject

The total volume of blood to be taken from each subject during the course of the study is 400 mL, as follows:

- Laboratory Assessments (including hepatitis and HIV screen): 20 mL x 5 timepoints = 100 mL

- PK determinations 5 mLx 57 time points = 285 mL
- ATA 7.5 mL x 2 time points = 15 mL.

8.12 Ophthalmological Evaluations

Ophthalmological evaluations will be performed on both eyes and will include the following, depending on the study day (See Appendix 3-Detailed List And Timing Of Procedures):

Local Ocular Tolerability (LOT) score:

- A global ocular discomfort score will be assessed by the subject using a self-administered 100 mm visual analogue scale (VAS) on which 0 means no symptoms and 100 means the worst possible discomfort. This evaluation is to be performed **before** any ophthalmic assessment at a given study visit.
- Specific ocular symptoms to be assessed with the VAS by the subject include:
 - foreign body sensation,
 - burning/stinging,
 - itching,
 - pain,
 - sticky feeling
 - blurred vision
 - photophobia

Best corrected distance visual acuity (BCDVA) measured using the ETDRS score

Subjects with a BCDVA score ≤ 0.00 LogMAR (≥ 83 ETDRS letters, 20/20 Snellen or 1.0 decimal fraction) in each eye at the Screening and Baseline visits are eligible for enrollment in the study.

Refraction and visual acuity measurements will be performed for all subjects by trained vision examiners only. The name and certification number of the vision examiner should be documented in the subjects' visual acuity (VA) worksheet (provided by the Sponsor) at each visit. Refraction should be conducted prior to visual acuity testing to obtain best-corrected vision as described below. Best-corrected visual acuity is measured at all trial visits using standard charts, lighting, and procedures. Best correction is determined by careful refraction at that visit according to the standard protocol for refraction as described below.

Refraction equipment required includes:

- Retroilluminated Light box and ETDRS 4 meter distance acuity chart set
- Trial lens frames
- Trial lens set with plus or minus cylinder lenses
- Jackson cross-cylinders of 0.25, 0.50, and 1.00 diopters
- Pinhole occluder
- Tissues or eye pads and tape
- A 1 meter rigid measuring stick

Visual acuity charts: Chart 1 is used for testing the visual acuity of the RIGHT eye; Chart 2 for testing the LEFT eye; and Chart R (or 3) for refraction only. Subjects should not be allowed to see any of the charts before the examination.

A distance of 4 meters is required between the subject's eyes and the visual acuity chart. With the box light off, not more than 15 foot-candles of light (161.4 Lux) should fall on the center of the chart. To measure the amount of light, the room is set up for visual acuity testing, but with the box light off. The light meter is placed at the fourth line from the top of the chart, with its back against the chart and the reading is taken. If more than one line available for testing visual acuity, the visual acuity of an individual subject should be measured in the same line at each visit, if possible. If different lines are used to test visual acuity, they must each meet the same standards.

Retroilluminated ETDRS charts are used in this trial. The illuminator box will be either wallmounted or mounted on a stand. The light box should be mounted at a height such that the top of the third row letter is 49 + 2 inches from the floor.

The visual acuity light box is equipped with two General Electric 20-watt fluorescent tubes and ballast. Each tube is partly covered by a 14-inch fenestrated sleeve, which is centered on the tube and open in the back. This serves as a “baffle” to produce even illumination over the testing chart. Because the illumination of fluorescent tubes diminishes by 5 percent during the first 100 hours and by another 5 percent during the next 2000 hours, new tubes should be kept on for 4 days (96 hours) continuously, and should be replaced once a year.

A sticker should be placed on the back of the light box, indicating the date when the present tubes were installed. A spare set of burned in bulbs should be available on site.

Detailed instructions for VA assessment

As a reminder, Charts 1, 2 and R (or 3) are used for testing the right eye, left eye, and refraction, respectively. Subjects should not see the charts until the test begins. The lens correction from the subject’s refraction should be in the trial frame worn by the subject.

All eyes must be tested at 4 meters first, even if the refraction was performed at 1 meter.

The subject should be seated comfortably directly in front of the chart so that the eyes remain at the 4 meter distance. Testing always begins with the right eye. The fellow (non-study) eye should be occluded with a folded tissue or eye pad lightly taped over the eye behind the trial frame serves as an effective occluder that allows eccentric fixation without inadvertent use of the covered eye. After testing the right eye, occlusion of the right eye should be done BEFORE Chart 2 is put up for testing the left eye.

The subject is asked to read the letters slowly, approximately one letter per second. The subject should be told that only one chance is given to read each letter, but may change their mind before moving to the next letter. If the subject is unsure about the identity of the letter, then the subject should be encouraged to guess.

The subject should begin by reading the top line of the chart and continue reading every letter on each smaller line, from left to right on each line. The subject should be encouraged to continue reading even if making mistakes. Each letter read is counted. The examiner circles every correct letter read and totals each line and the whole column (0 if no letters are correct) on the provided VA worksheet. An X is put through letters read incorrectly. Letters, for which no guess was attempted, are not marked. When a subject reaches a level where he/she cannot guess, the examiner may stop the test, provided that the subject has made errors on previous guesses, which is a clear indication that the best visual acuity has been obtained.

When a subject cannot read at least 20 letters on the chart at 4 meters, the subject is tested at 1 meter. The distance from the subject to the chart should be measured again using the rigid one meter stick. The distance is measured from the outer canthus to the center of the fourth letter (right eye) or the second letter (left eye) of the third line of the chart. The spherical correction in the trial frame should be changed by adding +0.75 to correct for the closer test distance. The subject may fixate eccentrically or turn or shake his/her head to improve visual acuity. Particular care should be taken to make sure the subject does not move forward when testing at 1 meter. The subject should be reminded to blink.

The examiner should not tell the subject if a letter was identified correctly. The subject may be encouraged by neutral comments, such as “good,” “next,” and “OK.”

The examiner should not stand close to the chart during testing. Attention should be focused on the subject and the VA worksheet. If the subject has difficulty locating the next line to read, the examiner may go up to the chart and point briefly to the next line to be read, but then must move away from the chart.

When 20 or more letters are read at 4 meters the visual acuity score for that eye is recorded as the number of letters correct at 4 meters plus 30 (refer to the VA worksheet). The subject gets credit for the 30 letters at 1 meter even though they did not have to read them. Otherwise, the visual acuity score is the number of letters read correctly at 1 meter plus the number, if any, read at 4 meters. If no letters are read correctly at either 4.0 meters or 1 meter, then the visual acuity score is recorded as “0.”

Clinically significant changes (or a clinically significant worsening) in BCDVA, which were observed the first time during study will be reported as adverse event.

External ocular examination (EOE): motility and eyelids

External Ocular Examination assesses the motility of the extraocular muscles and the appearance and function of the eyelids before the instillation of any dilating or anesthetic eye drops.

Clinically significant changes (or a clinically significant worsening) in EOE, which were observed the first time during study will be reported as adverse event.

Slit-lamp examination (SLE)

SLE to assess the eyelid margin, conjunctiva, cornea, anterior chamber, iris and lens. The Slit-lamp examination (SLE) must be performed before the instillation of any dilating or anesthetic eye drops or the fluorescein agent. The subject will be seated at the slit-lamp while being examined. Grading of the eyelids, lashes, conjunctiva, cornea, lens, iris and anterior chamber will be done according to the following scales:

Eyelid - Meibomian glands

Evaluation of the central ten Meibomian gland openings in the mid-portion of the upper eyelid:

- 0 = None (none are plugged).
- 1 = Mild (1 to 2 glands are plugged).
- 2 = Moderate (3 to 4 glands are plugged).
- 3 = Severe (All glands are plugged).

Eyelid - Erythema

- 0 = None (normal).
- 1 = Mild (redness localized to a small region of the lid(s) margin OR skin).
- 2 = Moderate (redness of most or all lid margin OR skin).
- 3 = Severe (redness of most or all lid margin AND skin).
- 4 = Very severe (marked diffuse redness of both lid margin AND skin).

Eyelid - Edema

- 0 = None (normal).
- 1 = Mild (localized to a small region of the lid).
- 2 = Moderate (diffuse, most or all lid but not prominent/protruding).
- 3 = Severe (diffuse, most or all lid AND prominent/protruding).
- 4 = Very severe (diffuse AND prominent/protruding AND reversion of the lid).

Lashes

- 0 = Normal.
- 1 = Abnormal (specify).

Conjunctiva – Erythema

- 0 = None (normal).
- 1 = Mild (a flush reddish color predominantly confined to the palpebral or bulbar conjunctiva).

2 = Moderate (more prominent red color of the palpebral or bulbar conjunctiva). 3 = Severe (definite redness of palpebral or bulbar conjunctiva).

Conjunctiva - Edema

0 = None (normal).

1 = Mild (slight localized swelling).

2 = Moderate (moderate/medium localized swelling or mild diffuse swelling).

3 = Severe (severe diffuse swelling).

4 = Very severe (very prominent/protruding diffuse swelling).

Lens

0 = No opacification (normal lens).

1 = Mild lens opacification.

2 = Moderate lens opacification.

3 = Severe lens opacification.

N/A = Subject with artificial lens

Iris

0 = Normal

1 = Abnormal.

Anterior Chamber Inflammation (Slit beam = 0.3 mm wide, 1.0 mm long)

0 = None (no Tyndall effect).

1 = Mild (Tyndall effect barely discernible).

2 = Moderate (Tyndall beam in the anterior chamber is moderately intense).

3 = Severe (Tyndall beam in the anterior chamber is severely intense).

Corneal findings of interest on the SLE include also the horizontal diameter of the cornea (measured in mm at the time of the SLE using a ruler).

Clinically significant changes (or a clinically significant worsening) in SLE, which were observed the first time during study will be reported as adverse event.

Corneal fluorescein staining (modified Oxford scale)

As grading scale of the corneal and conjunctiva damage, the NEI/Industry Workshop guidelines will be used [Reference: 2]. The cornea is divided into five sectors (central, superior, inferior, nasal and temporal), each of which is scored on a scale of 0–3, with a maximal score of 15. Both nasally and temporally, the conjunctiva is divided into a superior paralimbal area, an inferior paralimbal area and a peripheral area with a grading scale of 0–3 and with a maximal score of 9 for the nasal and temporal conjunctiva.

For a better reading it is also essential not to use an intense illumination beam, which may reduce the contrast and lead to an underestimation of grading [Reference: 3].

Clinically significant changes (or a clinically significant worsening) in corneal fluorescein staining, which were observed the first time during study will be reported as adverse event.

Tear Film Break-up Time (TFBUT)

Subjects with TFBUT < 8 seconds in either eye at the screening or baseline visit are NOT eligible for enrollment.

TFBUT will be measured by determining the time to tear break-up. The TFBUT will be performed after instillation of 5 µl of 2% preservative-free sodium fluorescein solution into the inferior conjunctival cul-de-sac of each eye. The subject will be instructed to blink several times to thoroughly mix the fluorescein with

the tear film. In order to achieve maximum fluorescence, the examiner should wait approximately 30 seconds after instillation before evaluating TFBUT. With the aid of a slit lamp at 10X magnification using cobalt blue illumination, the examiner will monitor the integrity of the tear film, noting the time it takes to form lacunae (clear spaces in the tear film) from the time that the eye is opened after the last blink. This measurement will be performed within 10 seconds maximum. The TFBUT will be measured twice during the first minute after the instillation of the fluorescein. If the 2 readings differ by more than 2 seconds a third reading is taken.

The TFBUT value will be the average of the 2 or 3 measurements.

Clinically significant changes (or a clinically significant worsening) in ECG, which were observed the first time during study will be reported as adverse event.

Schirmer test without anesthesia

Schirmer test without anesthesia is only required at the screening visit. Subjects with a Schirmer test without anesthesia ≤ 9 mm/5 minutes in either eye at the screening visit are NOT eligible for enrollment.

This test will be performed to measure aqueous tear secretion prior to the instillation of any dilating or eye drops. Both eyes may be tested at the same time.

This test will be conducted in a dimly lit room. While the subject looks upwards, the lower lid will be drawn gently downwards and temporally. The rounded bent end of a sterile strip will be inserted into the lower conjunctival sac over the temporal one-third of the lower eyelid margin. The test should be done without touching directly the Schirmer test strip with the fingers to avoid contamination of skin oils. The subjects will be instructed to close their eyes gently. After 5 minutes have elapsed, the Schirmer test strip will be removed and the length of the tear absorption on the strip will be measured (millimeters/5 minutes).

The wetting distance at 5 minutes for each eye will be recorded in the eCRF.

Fundus ophthalmoscopic (FO) examination

Fundus ophthalmoscopic (FO) examination will be performed to assess the vitreous, retina/macula/choroid, and optic nerve, including cup/disc ratio. Dilated FO will be performed at screening with non-dilated FO performed at other visits.

Clinically significant changes (or a clinically significant worsening) in FO, which were observed the first time during study will be reported as adverse event.

Intraocular pressure (IOP)

Subjects with IOP ≥ 22 mmHg in either eye at the screening or baseline visit are NOT eligible for enrolment,

Intraocular pressure (IOP) will be determined using Goldmann applanation tonometry.

Clinically significant changes (or a clinically significant worsening) in IOP, which were observed the first time during study will be reported as adverse event.

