4.1 Inclusion Criteria

To be eligible for inclusion into this study, each subject must fulfil the following inclusion criteria.

Each subject must meet all of the following inclusion criteria at the pre-study Screening visit (within 20 days prior to admission in the Unit for the dosing period) in order to participate in this study.

1. Male or female subjects of Japanese ethnicity, aged between 18 and 60 years inclusive, who must have all four Japanese grandparents who were born in Japan.
2. Subject has to be able to communicate well with the investigator, understands and complies with the requirements of the study, and understands and signs the written volunteer informed consent form.
3. Subject's systemic and ocular medical history must be considered normal in the opinion of the investigator at the Screening and Baseline visits.
4. Best corrected distance visual acuity (BCDVA) score ≤ 0.00 LogMAR (≥ 83 ETDRS letters, 20/20 Snellen or 1.0 decimal fraction) in each eye at the Screening and Baseline visits.
5. Normal anterior segment on external and slit lamp examination in both eyes at the Screening and Baseline visits.
6. Normal posterior segment on fundus ophthalmoscopic examination in both eyes at the Screening and Baseline visits.
7. Subject must be considered in good systemic health in the opinion of the investigator at the Screening and Baseline visits, as determined by:
 - a. Subject's body mass index is between 18.5 and 30.4 kg/m² inclusive
 - b. A pre-study physical examination with no clinically significant abnormalities.
 - c. Vital signs within clinically acceptable ranges for the purposes of the study (sitting systolic blood pressure [BP] ≥ 90 mmHg and ≤ 150 mmHg; diastolic BP ≥ 50 mmHg and ≤ 95 mmHg; heart rate ≥ 40 and ≤ 100 beats per minute; oral body temperature $\geq 35.5^{\circ}\text{C}$ and $\leq 37.5^{\circ}\text{C}$).
 - d. An ECG with no clinically significant abnormalities.
 - e. Pre-study clinical laboratory findings within normal range or not deemed clinically significant in the opinion of the investigator if outside of the normal range

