6.1 Randomisation

A total of 30 subjects will be randomized: 20 subjects on rhNGF treatment group and 10 on Vehicle treatment group.

Eligible subjects will be randomized at the Baseline Visit in a 2:1 ratio to a respective treatment group according to the randomization code and determined by the allocated randomization number. Randomization will be stratified by gender to ensure a balanced (2:1) gender distribution between treatment groups. With at least 6 subjects be recruited for each gender, it is ensured to have at least 4 male and 4 female subjects in the rhNGF group and 2 male and 2 female subjects in the Vehicle group.

Moreover, the study eye will be randomized for each subject to left and right eye.

During randomization, each subject will be allocated with randomization number. Together with the randomization number, the randomized study eye and associated kit number will be provided.

Randomization list and study eyes as well as associated kit numbers will be generated by a member of Cromsource SAS programming group not involved in the conduct of the study. A total of 60 kits (containing the treatment for right and left eye) will be supplied to the Pharmacy of the Clinical Unit.

Subjects will be assigned to treatment in numerical order. A tear-off label from the kit box, with the kit number, will be attached to the investigational product dispensing log.

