7.2.13 Secondary Safety Endpoints – Best Corrected Distance Visual Acuity (BCDVA)

Vision must be measured for each eye separately using ETDRS visual acuity chart at 4 meters (13 feet) and, if indicated, also at 1 meter (i.e. when less than 20 letters were read at 4m).

Clinically significant changes (or a clinically significant worsening) in BCDVA, which were observed the first time during study will be reported as adverse event.

In case both tables on the eCRF page have been completed (at 4 meter and at 1 meter) then the visual acuity score is the sum of the total number of correct letters from both tables. If only the table at 4 meter is completed and the overall number of letters read is 20 or above then the Visual Acuity Score is the number of total letters read at 4 meter plus 30.

If no letter were read at 4 and 1 meter, the best visual potential ability of the subject is selected from: a) count fingers; b) hand motion; c) light perception; or d) no light perception. The Visual Acuity Score is then set to 0.

The Snellen Equivalent is defined as the acuity equivalent for the smallest line with 1 or no error. The logarithm of the minimal angle of resolution (logMAR) is calculated as “- log (Snellen Equivalent)” with two decimals precisions. The logMAR ranges from 0.30 (20/10) to 1.60 (20/800) and an increase in logMAR reflects a worsening of visual acuity. If for a subject only ability for counting fingers is reported, logMAR will be set to 2.00; if for a subject only recognition of hand motion is reported, logMAR will be set to 3.00 (Holladay 1997).

Visual acuity is assessed for each eye at Screening Visit, Baseline Visit 0hr, D1 8hr, D2 Pre-Dose, D2 8hr, D3 Pre-Dose, D6 Pre-Dose, D6 8hr, FU1 0hr, FU2 8hr, FU3 0hr and are documented on the eCRF page “Best Corrected Distance Visual Acuity”.

The change from baseline will be derived for Visual Acuity Score and LogMAR per eye for all scheduled post-baseline visits as differences from Baseline (D-1 0hr).

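### The acuity instruction in Protocol 8.12 covers the fellow (non-study) eye instead of the eye not being tested, so it is wrong as written for left-study-eye subjects and cannot be applied at Screening or Baseline (minor)

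*Protocol*

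**What the plan says.** The instruction is in Protocol 8.12, under the detailed instructions for VA assessment. On the order of testing and which eye to cover it says: "Testing always begins with the right eye. The fellow (non-study) eye should be occluded with a folded tissue or eye pad". The changeover follows: "After testing the right eye, occlusion of the right eye should be done BEFORE Chart 2 is put up for testing the left eye". Earlier in 8.12 the charts are assigned by side: "Chart 1 is used for testing the visual acuity of the RIGHT eye; Chart 2 for testing the LEFT eye".

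The study eye is not a fixed side. Protocol 6.1 says: "Moreover, the study eye will be randomized for each subject to left and right eye". Elsewhere, for example in the synopsis and in 5.2 and 5.4.2, the fellow (non-study) eye is the eye that receives vehicle in every subject.

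Inclusion criterion 4 in Protocol 4.1 requires the acuity threshold to be met "in each eye at the Screening and Baseline visits". Protocol 5.4.2 masks subjects and the investigator/ophthalmologist to the study-eye randomisation. SAP 7.2.13 requires each eye to be measured separately and lists the assessment times. SAP 3.6, which sets out changes and refinements to the protocol, does not mention the occlusion rule.

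**The concern.** In a monocular acuity test, the eye to cover is the one not being read. The sentence instead names the eye by its treatment allocation. That happens to be the untested eye when the study eye is the right. It is the eye under test when the study eye is the left.

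Visual acuity score and LogMAR by eye are secondary safety endpoints (Protocol 10.1), and SAP 10.7.5 summarises both by study and non-study eye. If the sentence were followed to the letter in a left-study-eye subject, the right-eye score would in fact be read with the left eye. The fellow-eye reading would then be wrong, and a change in that eye could go unseen.

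**Working it through.** The plan gives no figure on this point to reproduce. The check sets the study eye against the eye under test, and the timing of study-eye assignment against the acuity schedule.

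**Step 1: which eye is covered.** The order is right then left in every subject. The occlusion sentence governs the first test and the changeover sentence governs the second.

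| Study eye | First test: right eye, Chart 1 | Second test: left eye, Chart 2 |
|---|---|---|
| Right | Fellow eye is the left; left covered; works | Right covered; works |
| Left | Fellow eye is the right; the eye under test is covered; fails | Right covered; works |

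One of the four cells fails: the right-eye (fellow-eye) test in left-study-eye subjects. In that cell the two sentences also conflict, since the changeover takes it that the right eye was open until its test was finished. Both study-eye cells work: right eye first in right-study-eye subjects, left eye second in left-study-eye subjects.

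**Step 2: when a study eye exists.** SAP 7.2.13 lists 11 acuity assessments: Screening, Baseline 0hr, and then D1 8hr, D2 Pre-Dose, D2 8hr, D3 Pre-Dose, D6 Pre-Dose, D6 8hr, FU1, FU2 and FU3. That is 2 + 9 = 11. Protocol 6.1 places randomisation at the Baseline Visit for eligible subjects, and 7.2 lists it under Treatment Day 1. Those two passages should be reconciled, but the result here is the same under either. Baseline acuity is part of eligibility, so it precedes assignment of the study eye. At 2 of the 11 assessments there is no non-study eye to cover in any subject.

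**Step 3: whether the rule can be followed afterwards.** Under 5.4.2 the investigator/ophthalmologist does not know the study eye, and an examiner masked in that way cannot apply the rule. Protocol 6.1 does say that the randomised study eye is provided with the randomisation number, without saying to whom. An examiner who did know it would meet the failing cell in Step 1.

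**Step 4: size on the literal reading.** The label footnote in Protocol 5.3.1 says the list is balanced by study eye, among other factors, but no left:right ratio is given. Assuming 1:1:

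- left-study-eye subjects: 30 × 0.5 = 15
- fellow-eye readings in the failing cell: 15 × 9 = 135, of 30 × 9 = 270
- of these, in the rhNGF group: 20 × 0.5 × 9 = 90
- in the vehicle group: 10 × 0.5 × 9 = 45
- study-eye readings in a failing cell: 0 of 270

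These counts show how many readings the wording touches. They do not predict how many would be wrong.

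**The case against.** The strongest reply is that nobody would test this way. Charts go by right and left. The changeover sentence shows that the right eye is meant to be open for its own test. The stated purpose of the pad is to prevent use of the covered eye. SAP 7.2.13 asks for each eye separately, and 8.12 limits testing to trained vision examiners with certification numbers recorded. Padding the right eye and then recording a right-eye score would be noticed at once. This stands, and it is why the practical effect is probably small. It does not make the sentence correct: good practice would require departing from it in about half the subjects after randomisation, and before randomisation it names no eye at all.

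A reader might infer more than the documents support:

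- *That about 135 readings will be corrupted.* Nothing in the documents suggests this would happen, and the masking in 5.4.2 makes it less plausible still.
- *That the vehicle eye would simply copy the active eye.* Ten of the 30 subjects receive vehicle in both eyes, so this could apply to at most the 90 rhNGF-group readings, and only on the literal reading.
- *That sight-threatening events in the study eye could be missed.* Study-eye readings are correct in every case in the table, so the acuity-loss criterion in Protocol 9.1 still works for that eye.
- *That the number of left study eyes could vary as in independent coin tosses.* The list is described as balanced by study eye, so simple binomial variation does not apply.
- *That the VA worksheet repeats the error.* The worksheet is not among the documents, so nothing can be said about its wording.

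**Conclusion.** The occlusion sentence in Protocol 8.12 is wrong as written, and the severity is minor. It covers the eye under test in left-study-eye subjects and contradicts the sentence after it. It has no meaning at the Screening and Baseline eligibility tests, and it cannot be followed by an examiner masked to the study eye.

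On the literal reading the damage is confined to fellow-eye acuity in left-study-eye subjects, about half the sample at 9 tests each. That size rests on an assumed 1:1 split. The structural findings (the failing cell, the 2 assessments with no study eye, and the conflict with masking) do not depend on it.

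Acuity is summarised descriptively with no inferential analysis, and the only within-subject between-eye difference the SAP plans is for the VAS tolerability scores. Sample size and the planned analyses are unaffected.

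**What to change.** In Protocol 8.12, replace the reference to the fellow (non-study) eye in the occlusion sentence with: *The eye not being tested should be occluded*. Add that the left eye is covered for Chart 1 and the right eye for Chart 2, at every visit including Screening and Baseline. This agrees with the changeover sentence and the chart assignment already in the section, and it needs no knowledge of the study eye. The cost is one sentence, with no added procedure and no change to the schedule or the SAP analyses.
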